**VOICE THERAPY WITH A SEMI-OCCLUDED VOCAL TRACT:
FROM CURRENT CHALLENGES TO NEXT LEVEL EFFICACY STUDIES**

Protocol and statistical analysis plan

Document date: March 3, 2023

PROTOCOL

This study has been approved by the Ethics Committee of Ghent University Hospital (BC-09807).

Participants

Female students in the first year of study toward a bachelor degree in Logopaedic and Audiological Sciences at Ghent University (academic year 2021-2022), will be recruited for this study by convenience sampling. They will all provide written informed consent. Exclusion criteria are: an organic vocal fold pathology diagnosed by a specialized otorhinolaryngologist, smoking, pregnancy and hearing problems.

Design

A randomized controlled trial will be used. Participants will be assigned randomly to one of three experimental groups or a control group: (1) straw phonation (SP) in air, (2) SP in 2cm water, (3) SP in 5cm water or (4) /u/ phonation with similar soft onset and slightly pursed lips as in SP but without a straw (control group). An online random number generator will be used for this procedure.

Material and methods

Straw phonation material

Ecologic compostable wheat stirring straws with a diameter of 3mm and a length of 20cm will be selected for all experimental groups. SP in water will be performed in reusable cups, and the water depth (2cm or 5cm) will be set by drawing a line on the straw.

Preparatory phase

Before the experiment, in the second week of the academic year, all students will receive one group SP workshop of 20 min guided by an experienced voice therapist ([name]). The aim of this session is to strive for a correct and comfortable SOVT production prior to the actual experiment. First, focus will be on an eutonic posture in sitting position and costo-abdominal breathing. Participants will be instructed to breath in through the nose and blow out through the mouth without phonation. Second, they will be asked to repeat this but now adding phonation on a [ɔ] vowel with soft onset [hhhɔɔɔ] during exhalation, at habitual comfortable pitch and loudness. Afterwards, both step one (without phonation) and step two (with phonation) will be repeated with the straw. Attention will be drawn to sensory feedback, forward focus, and avoidance of hyperfunction. At the preparatory phase, students will be unaware of their group assignment and will be specifically instructed to not practice the exercises at home.

Flexible strobovideolaryngoscopy and phonatory tasks

In the third and fourth week of the academic year, all students will undergo flexible SVL by a specialized otorhinolaryngologist ([name] or [name]) using an EndoFLEX Spectar laryngoscope (Xion Medical). The participants will be examined in seated position with the head upright and without administration of topical anesthesia. During the examination, they will be asked to phonate an [u] vowel at habitual pitch and loudness (baseline), followed by the specific SOVT exercise of their group assignment. For the SOVT phonation, they will be instructed to produce an [u] vowel at habitual pitch and loudness with soft onset and slightly pursed lips through the stirring straw (either in air, 2cm water or 5cm water) or without a straw (control group). The [u] vowel will be selected for all phonatory tasks (baseline and SOVT, both in the experimental group and the control group) so that potential differences are more certainly attributable to SP and not to differences in vowel production. The same voice therapist ([name]) will guide them through these phonatory tasks, together with a master's student ([name]) for practical support.

Visual-perceptual ratings

After data collection, all video samples will be evaluated randomly and blindly by an otolaryngology resident ([name]) and a speech-language pathologist specialized in voice ([name]). Evaluations will be standardized by use of the Voice-Vibratory Assessment with Laryngeal Imaging (VALI) rating form for stroboscopy (Poburka et al., 2017). In advance, a half hour training session will be provided in which each parameter will be clarified with the definition, a high-quality graphic, and two video examples.

After the training, the assessors will first independently evaluate each video sample on a self-paced basis, after which a consensus evaluation will be reached. Ten percent of the samples will be randomly repeated to assess intrarater reliability. The video samples will be presented without audio to prevent bias of the participant's voice quality on the judges' ratings.

The parameters to be evaluated are glottal closure (complete, anterior gap, posterior gap, hourglass, spindle gap, irregular, or incomplete), amplitude (magnitude of lateral movement of the vocal folds, in %), mucosal wave (magnitude of lateral movement of the mucous membrane in %), vertical level (on-plane, off-plane left lower, or off-plane right lower), nonvibratory portion (adydynamic segments of tissue that appear stiff, in %), anteroposterior (AP) and mediolateral (ML) supraglottic activity (constriction of the supraglottic structures, rated 0 – 5 with the aid of concentric circles), free edge contour (normal, convex, concave, irregular, or rough), phase closure (open phase predominates, nearly equal, or closed phase predominates), phase symmetry (the degree of symmetry between the left and the right vocal folds in terms of opening and closing, in %), and regularity (consistency of averaged stroboscopic cycles, in %) (Poburka et al., 2017).

STATISTICAL ANALYSIS PLAN

The data will be analyzed statistically by SPSS version 28 (SPSS Corporation, Chicago, IL, USA) at $\alpha = 0.05$.

To determine the interrater reliability of the visual-perceptual ratings, a two-way mixed, consistency, average-measures intraclass correlation coefficient (ICC) will be calculated for the continuous variables, and a Cohen's kappa (K) will be used for the nominal variables (Hallgren, 2012; Koo & Li, 2016). Intrarater reliability will be determined using a two-way mixed, absolute agreement, single-measures ICC for the continuous variables, and a Cohen's K will be used for the nominal variables (Hallgren, 2012; Koo & Li, 2016).

Linear mixed model analyses will be used to compare the groups over phonatory condition (habitual [u] phonation vs SOVT phonation) on each continuous variable using the restricted maximum likelihood estimation and scaled identity covariance structure. Group, Phonatory Condition and Phonatory Condition * Group interaction will be determined as fixed factors. A random intercept for subjects will be included. Model assumptions will be checked by inspecting whether residuals were distributed normally. Within-group effects of Phonatory Condition will be determined by posthoc pairwise comparisons. Marginal homogeneity tests will be used to compare nominal variables between habitual /u/ phonation and SOVT phonation within groups.

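### The four nominal parameters get no comparison between randomised arms, and the interaction tests on the continuous parameters have no primary outcome or multiplicity rule

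*Combined protocol and SAP*

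**What the plan says.** The Design section randomises participants to three straw arms (air, 2 cm water, 5 cm water) or to a control arm: "u/ phonation with similar soft onset and slightly pursed lips as in SP but without a straw (control group". In the section on strobovideolaryngoscopy and phonatory tasks, each participant first phonates a habitual [u] and then performs the task of her arm.

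The section on visual-perceptual ratings lists 11 parameters without ranking them:
- Five are in per cent: amplitude, mucosal wave, nonvibratory portion, phase symmetry and regularity.
- Two are supraglottic activity scores, AP and ML ("constriction of the supraglottic structures, rated 0 – 5 with the aid of concentric circles").
- Four are categorical: glottal closure, vertical level, free edge contour and phase closure.

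The Statistical Analysis Plan sets one significance level: "The data will be analyzed statistically by SPSS version 28 (SPSS Corporation, Chicago, IL, USA) at $\alpha = 0.05". For continuous variables, "Linear mixed model analyses will be used to compare the groups over phonatory condition (habitual [u] phonation vs SOVT phonation) on each continuous variable", with a condition-by-group interaction among the fixed effects. It then adds: "Within-group effects of Phonatory Condition will be determined by posthoc pairwise comparisons". For the categorical parameters the only test is: "Marginal homogeneity tests will be used to compare nominal variables between habitual /u/ phonation and SOVT phonation within groups".

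The plan does not name a primary outcome, a testing order or an adjustment. It does not list which variables count as continuous, or say whether the post hoc comparisons depend on a significant interaction.

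**The concern.** The control arm shares the vowel, onset and lip posture of the straw arms, so that what remains between arms can be put down to the straw. That works only if the analysis compares arms. For the four nominal parameters it does not. A before-and-after change in a straw arm mixes the straw with the changed onset, the lip posture and the fixed task order, and the control arm is exposed to the last three as well. Readers would be left to set a significant result in one arm beside a non-significant result in another, which is not a test of the difference between them. The within-group post hoc comparisons of the continuous parameters have the same limit, although there the interaction does supply a comparison of arms.

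The second matter is how many interaction tests share the 0.05. That level holds for each test singly. It does not hold for the set of parameters from which a conclusion about straw phonation would be drawn.

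**Working it through.** The plan states no sample size, power or familywise error rate, so it has no figure to reproduce beyond the 0.05 per test.

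**Count of tests** (one value per parameter per video sample assumed)

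| Parameters | Number | Within-arm tests (4 arms) | Between-arm tests |
|---|---|---|---|
| Per cent scale | 5 | 5 × 4 = 20 | 5 interactions |
| 0 to 5 scale, if continuous | 2 | 2 × 4 = 8 | 2 interactions |
| Categorical | 4 | 4 × 4 = 16 | 0 |

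If the 0 to 5 ratings are not continuous, the interactions number 5, and those two ratings have no fitting method, because the SAP provides only for continuous and nominal variables.

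**Attribution.** Write the mean change in a straw arm as *s* + *c* and in control as *c*, where *s* is the straw effect and *c* collects onset, lip posture and order. A within-arm test asks whether *s* + *c* = 0. The straw question is whether *s* = (*s* + *c*) − *c* = 0, which needs both arms in one test.

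**Illustration of the pattern that would mislead.** Let *s* = 0 in every arm, with the same true shift *c* in all four. Let each within-arm test have power *p*, independently across arms.
- A given straw arm significant and control not: *p*(1 − *p*).
- At least one of three straw arms significant and control not: (1 − *p*)[1 − (1 − *p*)³].

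| Assumed *p* | Given straw arm | At least one of three |
|---|---|---|
| 0.3 | 0.21 | 0.46 |
| 0.5 | 0.25 | 0.5 × (1 − 0.125) = 0.44 |
| 0.8 | 0.16 | 0.20 |

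**Interactions.** With four arms and two conditions, each interaction test has 3 degrees of freedom. If the tests are independent and no effect exists:
- 7 tests: 1 − 0.95⁷ = 0.302
- 5 tests: 1 − 0.95⁵ = 0.226

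The ratings are probably correlated, and the documents give no correlations. Simulation (200,000 runs, equal assumed correlation between parameters) gives the chance of at least one false positive:

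| Assumed correlation | 0 | 0.3 | 0.5 | 0.7 | 0.9 |
|---|---|---|---|---|---|
| 7 tests | 0.302 | 0.275 | 0.237 | 0.188 | 0.118 |
| 5 tests | 0.227 | 0.211 | 0.188 | 0.152 | 0.106 |

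**Price of familywise control.** The full set of straw-versus-control contrasts is 11 × 3 = 33. The first Holm step is at 0.05/33 = 0.0015, two-sided critical value 3.172. By normal approximation, a contrast with 80% power at 0.05 keeps Φ(1.960 + 0.842 − 3.172) = Φ(−0.370) = 0.356.

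**The case against.** The strongest reply is that this is a single-session imaging comparison in students without organic vocal fold pathology, and that the plan states no confirmatory claim. Familywise control over dozens of contrasts is then a matter of judgement, and at the first step it would more than halve the power of a contrast that has 80% at 0.05. That stands. It is why the fix does not require an adjustment, only that the exploratory status be stated and the p-values labelled.

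It can also be said that the interaction already compares arms. For the continuous parameters this is right, so it would be wrong to read the plan as having no randomised comparison at all. The interaction does not show which straw arm differs from control, and it does nothing for the nominal parameters.

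Two stronger readings are tempting but not supported:
- A reader might count all within-arm tests in the straw arms (7 × 3 = 21) and quote 1 − 0.95²¹ = 66% as a false positive rate. That assumes no change between tasks in any arm, which sits badly with the task change and fixed order just described. A significant within-arm result may be a real change. The fault is that it cannot be attributed to the straw.
- A reader might infer from "Document date: March 3, 2023" and the 2021-2022 academic year that the tests were chosen after the results were seen. The dates suggest that the examinations came first. The documents do not say whether the ratings were known.

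**Conclusion.** The concern holds. The firmer part is the nominal one, which rests on the text and on no numerical assumption: four of 11 parameters have no between-arm test, so the plan as written cannot separate a straw effect on them from an effect of onset, lip posture or order. The 44% figure only illustrates this. It assumes 50% within-arm power and an equal shift in all arms.

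The second part is a matter of labelling and interpretation. Without a primary outcome or multiplicity rule, the chance of at least one false positive interaction is 30% to 12% for 7 tests, or 23% to 11% for 5, under a global null and assumed correlations from 0 to 0.9. Treating the 0 to 5 ratings as continuous is an inference. If any parameter is scored separately for the left and right folds, the counts rise. The absence of an adjustment might be read as an error in itself. The documents do not support that, because they claim no confirmatory result. What is missing is a statement of how the tests are to be read.

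**What to change.** 1. For each nominal parameter, add a straw-versus-control comparison of the direction of change: toward, unchanged, or away from a reference category. An exact permutation test on a −1/0/+1 score would serve. Fix the reference categories without reference to results, and run the test for all four parameters whatever the results.
2. List which variables are modelled as continuous. For each, report the three straw-versus-control differences in change with 95% confidence intervals. These are the interaction coefficients of the planned model with control as reference. Base claims about straw phonation on between-arm contrasts. If the AP and ML ratings are not continuous, give them a between-arm test too.
3. Label all within-arm tests, marginal homogeneity tests included, as descriptive.
4. State that the omnibus interaction p-values and any straw-versus-straw contrasts are unadjusted and descriptive.
5. Label the between-arm p-values as unadjusted and the study as exploratory. If confirmatory claims are wanted, apply Holm to the full fixed family of 33 straw-versus-control contrasts, date that decision, and state whether ratings were known.

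The cost is SAP wording, different contrasts from models already planned, and one small added analysis. No new data are needed. Collapsing categories loses shifts between types of glottal gap. Only if Holm is chosen is there a loss of power: a contrast with 80% at 0.05 keeps about 36% at the first of 33 steps. Absolute power cannot be given, because no sample size is stated.

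### The three straw arms differ only in air, 2 cm or 5 cm water, but the plan names no comparison of change between them: only a four-arm interaction and within-arm tests

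*Combined protocol and SAP*

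**What the plan says.** The Design section randomises to three straw arms, "1) straw phonation (SP) in air, (2) SP in 2cm water, (3) SP in 5cm water", and to a control arm that phonates /u/ without a straw. Under Straw phonation material, one straw type "with a diameter of 3mm and a length of 20cm will be selected for all experimental groups", and "the water depth (2cm or 5cm) will be set by drawing a line on the straw". As designed, the straw arms therefore differ from one another only in medium and depth.

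The Statistical Analysis Plan says: "Linear mixed model analyses will be used to compare the groups over phonatory condition (habitual [u] phonation vs SOVT phonation) on each continuous variable". The fixed effects follow: "Group, Phonatory Condition and Phonatory Condition * Group interaction will be determined as fixed factors". The one follow-up named is: "Within-group effects of Phonatory Condition will be determined by posthoc pairwise comparisons". Nominal outcomes get marginal homogeneity tests inside each arm and nothing between arms.

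The plan names no contrast between straw arms, no between-group post-hoc comparison and no multiplicity rule. The documents give no sample size, primary outcome or hypothesis about water or depth.

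**The concern.** Someone reading the results will want to know whether water, or more water, alters the laryngeal response compared with the straw in air. The plan offers two results that look relevant, and neither answers that question.

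The first is the Group by Phonatory Condition interaction. It tests whether all four arms have the same mean change. If the straw arms shift equally and the control does not, it should reject, and that says nothing about water or depth.

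The second is the set of within-arm tests. Significance at 5 cm but not at 2 cm is not evidence that 5 cm differs from 2 cm, because two arms with the same true effect will often fall on opposite sides of 0.05.

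At stake is whether any statement about water or depth rests on an estimated between-arm difference with its uncertainty, or on a pattern of separate p-values.

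**Working it through.** The plan gives no power or sample-size figure, so there is nothing to reproduce. The figures below are illustrative.

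**Inputs from the documents.** Four arms; two phonatory conditions per participant; alpha 0.05; a random intercept per subject.

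**Assumptions.** Equal arms of n = 10, 15 or 20; complete pairs; two-sided tests; effects in units of the SD of the within-person change (SOVT minus [u]); pooled error with 4n − 4 df.

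**1. Degrees of freedom.** The interaction has (4 − 1)(2 − 1) = 3 df, and one of the four levels is the control. With balanced pairs it equals a one-way ANOVA on the change scores. A simulated data set confirmed this: the REML Wald chi-square divided by 3 was 3.198, and the ANOVA F was 3.198.

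**2. The interaction when water and depth do nothing.** Let each straw arm change by 0.8 SD and the control by 0. The mean is (3 × 0.8)/4 = 0.6, and the sum of squares about it is 3 × 0.2² + 0.6² = 0.48. The noncentrality is n × 0.48, which is 7.2 at n = 15. The noncentral F gives 57% rejection at n = 15 (38% at n = 10, 72% at n = 20). A contrast between straw arms rejects in 5%.

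**3. Per-arm p-values when the straw arms are identical.** If each arm is significant with probability p, exactly one of two is significant with probability of about 2p(1 − p). At n = 15 and 0.5 SD, p = 0.479, which gives 2 × 0.479 × 0.521 = 0.499. Simulation gives 0.490, slightly lower because the arms share one error estimate. With 200,000 simulated trials per setting, all straw arms at the stated effect and control at 0:

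| n per arm | Effect (SD) | Exactly one of 2 cm and 5 cm significant | Same, and interaction significant |
|---|---|---|---|
| 10 | 0.5 | 43.3% | 9.6% |
| 10 | 0.6 | 47.7% | 11.9% |
| 10 | 0.7 | 47.1% | 13.7% |
| 15 | 0.5 | 49.0% | 12.8% |
| 15 | 0.6 | 45.7% | 14.9% |
| 15 | 0.7 | 35.8% | 14.3% |
| 20 | 0.5 | 47.1% | 14.9% |
| 20 | 0.6 | 36.4% | 14.7% |
| 20 | 0.7 | 22.4% | 11.5% |

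**4. Is there a power argument?** Suppose change rises with depth (air 0, 2 cm 0.4, 5 cm 1.0 SD) and control equals air. A 1-df linear contrast (scores 0, 2, 5; coefficients −7, −1, 8) has 59/77/88% power at n = 10/15/20, and the 3-df interaction has 52/73/86%. The gain is 7, 4 and 2 points. If instead any water adds 1.0 SD, then at n = 15 the linear contrast has 70%, water versus air 87%, and the interaction 90% with control equal to air (74% with control at 0.5 SD). The advantage is small or reversed, depending on where the control lies.

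**5. Error cost of adding contrasts.** With identical straw arms, three unadjusted contrasts (water versus air, 5 cm versus 2 cm, linear trend) give at least one false positive in about 11% of trials per parameter. The trend is a combination of the other two, so it adds error without adding a question. The first two are orthogonal: (−1 × 0) + (½ × −1) + (½ × 1) = 0. Unadjusted, that pair errs in about 10%; with Holm, in about 5%.

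**The case against.** The best counter-argument is that the depth question is the reader's own. No objective mentions water, depth or dose response. The one rationale given, for using the same vowel throughout, concerns attributing differences to straw phonation, which is straw versus no straw. This stands: the aim is inferred from the arms. Treating the arms as a dose series goes further still, because moving from air to water changes the medium as well as the depth, so scoring air as 0 cm is an assumption.

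A reader might infer that the trial cannot validly answer a depth question at all. The documents do not support that. The planned model compares the groups and estimates every arm-by-condition mean, so any straw-arm contrast can be taken from it without new data. What is missing is the prespecified contrast.

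A reader might also infer that a false depth effect will often be claimed. The plan nowhere says that discordant per-arm p-values will be read that way, and it does not say whether within-arm tests depend on a significant interaction. The 22–49% range assumes no such dependence; with it, the range is about 10–15%. Both are frequencies of a misleading pattern, not predictions of what the authors will write.

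Finally, a reader might infer that the omnibus test wastes power on a 1-df question. Step 4 does not bear this out.

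The core of the concern survives: the only follow-up named is within arms, and it cannot show that two straw arms differ.

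**Conclusion.** The concern holds as a gap in prespecification. The plan builds three arms that differ only in medium and depth, and names no comparison of change among them. A significant interaction need not involve the straw arms differing from each other, and split within-arm results are common when they do not differ: about 22–49% of trials for the 2 cm and 5 cm pair, or about 10–15% if the interaction must also be significant. These figures rest on assumed arm sizes of 10–20, equal straw effects of 0.5–0.7 SD, no change in control, and pooled error.

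It is a worthwhile, cheap improvement and not a fatal flaw. It matters to the extent that the investigators intend to say anything about water or depth, which the documents do not state. The case for it is a valid, interpretable between-arm estimate. It is not a power gain, and it does not need an ordered trend.

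**What to change.** In the mixed model for each continuous parameter, prespecify two orthogonal contrasts of change (SOVT minus [u]) among the straw arms:

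- the mean of 2 cm and 5 cm water versus air;
- 5 cm versus 2 cm water.

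Report each with a 95% CI. Apply a simple multiplicity rule to the pair, for example Holm, or test the pair only if the 2-df test of equal change across the three straw arms is significant. State that conclusions about water or depth rest on these contrasts and not on which within-arm tests reach 0.05. Leave out a linear trend that scores air as 0 cm, or label it exploratory.

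The cost is one paragraph in the plan and a few contrast lines in a model already to be fitted, with no new data. The downside is two more contrasts for each of the seven continuous parameters, 2 × 7 = 14 in all, in a plan without a primary outcome; the rule above covers only the pair within a parameter. The plan is dated March 2023 and the intake is academic year 2021–2022, so data may already exist. If they have been analysed, the contrasts should be reported as added afterwards.

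This does not repair the four nominal parameters (glottal closure, vertical level, free edge contour, phase closure). They have within-arm tests only and no between-arm comparison of any kind.

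### Do the within-group tests need a check that change is equally variable in all four arms?

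*Combined protocol and SAP*

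**What the plan says.** The section Statistical Analysis Plan specifies one linear mixed model for each continuous outcome, fitted "using the restricted maximum likelihood estimation and scaled identity covariance structure", with a random intercept per participant and fixed effects for group, phonatory condition and their interaction. The stated purpose is to compare the groups across the two conditions. Then: "Within-group effects of Phonatory Condition will be determined by posthoc pairwise comparisons". The one diagnostic given is: "Model assumptions will be checked by inspecting whether residuals were distributed normally". Nothing is said about residual spread by arm, arm-specific variances, robust standard errors or a fallback.

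Three protocol sections bear on whether spread might differ:

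- **Design** describes three straw arms and a strawless control. On allocation it says only "An online random number generator will be used for this procedure".
- **Flexible strobovideolaryngoscopy and phonatory tasks** holds the task constant: "The [u] vowel will be selected for all phonatory tasks". The same therapist guides every participant.
- **Visual-perceptual ratings** lists bounded outcomes, such as 0-5 supraglottic activity and "nonvibratory portion (adydynamic segments of tissue that appear stiff, in" percent. Under Participants, students with "an organic vocal fold pathology diagnosed by a specialized otorhinolaryngologist" are excluded, so some of these ratings may sit near an end of their scale.

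**The concern.** Each participant contributes two measurements, so the model reduces to one change score per person. The random intercept cancels from the change, and the identity structure then gives change the same variance in every arm. A within-group test therefore divides an arm's mean change by a standard error built from all four arms.

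If the arms differ in spread, that standard error is too small in the more variable arms and too large in the others. The control task is close to the baseline task, whereas the other arms add a straw in air or water, so it is natural to suspect more variable change with a straw. The tests would then be somewhat liberal in the straw arms and conservative in control. A finding that the straw arms changed and control did not could partly reflect pooling. A larger sample would not remove this, and a normality check may miss it.

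**Working it through.** **Inputs.** From the SAP: alpha 0.05 (two-sided assumed), four arms, two measurements per participant, random intercept, scaled identity residual. The documents give no SD, arm size or effect, so there is no planned figure to reproduce. All SD ratios and arm sizes below are assumptions.

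**Which standard error the plan uses.** With residual variance σ², Var(change) = 2σ² in every arm. A fit of the planned model to simulated data (12 per arm, true change SDs 4, 8, 8, 16) gave 2.420 as the within-group standard error in all four arms. That equals the pooled value; the arms' own values were 0.75, 1.36, 1.89 and 4.18. The structural claim is correct.

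**Error rate if spreads differ.** With equal arms and no true change, the rejection rate in arm g is approximately 2 × [1 − Φ(1.96 × s_p / s_g)], where s_p² is the mean of the four change variances.

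For control SD 1 and straw SD 1.5: s_p² = (1 + 3 × 2.25)/4 = 1.9375, so s_p = 1.392.
- Control: 1.96 × 1.392 = 2.728, giving 0.6%.
- Straw arms: 2.728/1.5 = 1.819, giving 6.9%.

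Simulation at 12, 15 and 20 per arm:

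| Straw:control SD ratio | Control | Each straw arm | Interaction F |
|---|---|---|---|
| 1.17 | 2.8-2.9% | 5.7-5.9% | 5.1-5.2% |
| 1.27 | 1.8-1.9% | 6.2-6.3% | 5.2% |
| 1.5 | 0.7-0.8% | 6.7-7.0% | 5.2-5.3% |

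The first two ratios arise if 70% or 50% of the control change variance is rating error common to all arms and the rest has SD ratio 1.5: √(0.7 + 0.3 × 2.25) = 1.17 and √(0.5 + 0.5 × 2.25) = 1.27.

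**The mechanism the documents support.** On a rating at its floor, an arm whose mean moves also spreads out. Suppose the rating rises by 1 in 10% of control and 40% of straw participants. The SDs of change are √(0.1 × 0.9) = 0.30 and √(0.4 × 0.6) = 0.49.

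For a paired test using the arm's own variance, with k of n participants changing and p = k/n, t² = (n − 1)p/(1 − p). At n = 12 the critical value 2.201 requires p/(1 − p) > 4.844/11 = 0.440, so k ≥ 4. At n = 15, 2.145 requires p/(1 − p) > 4.600/14 = 0.329, again k ≥ 4. The binomial probabilities of k ≥ 4 give the own-arm column; the planned column is simulated.

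| n per arm | Arm | Planned test rejects | Own-arm test rejects |
|---|---|---|---|
| 12 | control | about 2.8% | 2.6% |
| 12 | straw | 83% | 77% |
| 15 | control | 5.6% | 5.6% |
| 15 | straw | 91% | 91% |

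Planned 95% intervals cover 93-94% in the straw arms and more than 99% in control. Own-arm intervals cover only 72-79% in control, because nobody changes, and the estimated variance is zero, with probability 0.9^12 = 28% or 0.9^15 = 21%.

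**Cost of arm-specific tests elsewhere.** With normal changes, a straw change of 0.6 control SDs and SD ratio 1.5, power falls from 32% to 24-25% at n = 12 and from 38-39% to 30% at n = 15. Part of that gap arises because the planned test runs at about 7%. With equal SDs the loss is from 53% to 47% and from 63% to 58%.

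**The case for a change.** The strongest case for a change has four parts.

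First, the distortion could exceed the table. If one arm alone has 1.5 times the SD of the others, s_p² = (3 + 2.25)/4 = 1.3125, and that arm's test rejects about 13% under no change; at twice the SD, about 19%. This arithmetic stands. Nothing in the documents points to one arm standing out to that degree, and the common vowel, the common therapist and blinded consensus rating point the other way.

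Second, normality is a poor proxy for equal spread. With 15 per arm and all three straw arms at ratio 2, a Shapiro-Wilk test flagged 9% of data sets and a Brown-Forsythe test 35%. That stands too, but the second figure also shows that a variance test would miss most such cases at this size.

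Third, arm sizes may be unequal, since no blocking is mentioned. With unrestricted allocation of 48 or 60 participants and control 1.5 times as variable as the straw arms, the interaction test rejects 5.8% or 5.7% on average, and 8.5% or 7.8% when control falls in its smallest decile. With the straw arms the more variable, it rejects about 5.4% on average, and 7.1% or 6.8% when control is in its largest decile. The averages are close to nominal; the higher values need several unfavourable assumptions together.

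Fourth, the remedy is a few lines of text. But arm-specific standard errors would have to be withheld from floor-bound ratings, the very outcomes for which unequal spread has a rationale. Elsewhere they cost power, and no clear minimum number of changes suggests itself for deciding where to apply them. Moreover, in an arm whose mean has moved off the floor, no change is already false, so an inflated type I error is not the harm there.

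**Conclusion.** No change to the plan. It is true that normality is the only check stated and that the within-group tests rest on one variance of change across arms. Nothing in the documents shows that the variances differ, and the common task and blinded rating favour similar spread. At assumed SD ratios of 1.17 to 1.5 with equal arms, the straw-arm tests run at about 6-7% instead of 5%, control is conservative, and the interaction test stays within about 0.3 percentage points of nominal. In the floor example the planned and arm-specific tests lead to nearly the same decisions, while arm-specific intervals do worse in control.

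What remains is ordinary practice: an analyst inspecting residuals will look at spread by group, and a results table will give arm sizes and the SD of change in each arm. Readers can then judge the pooling for themselves without an amended SAP. The conclusion assumes no single arm is far more variable than the rest; those descriptive figures would reveal it if one were.
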